10.3.7. Analysis of the safety variables

This section was modified with Amendment 3. For details, see Section 15.2.

The analysis of the primary safety variable is performed on the Full Analysis Set (FAS) under the ITT data scope — that is, events are analyzed irrespective of their time of occurrence relative to termination of assigned study treatment strategy. Follow-up is censored at the last date of known outcome status or at the efficacy cut-off date, whichever comes first.

Kaplan-Meier estimates of cumulative risk and cumulative hazard functions for the primary safety variable are provided to evaluate the timing of event occurrence in the different treatment groups and the consistency of the respective treatment effects for all time points.

If the proportional hazards assumption holds for the primary safety variable, hazard ratio and corresponding two-sided 95% confidence intervals are estimated based on a Cox proportional hazards models.

On treatment analyses, pre-NOAF and post-NOAF analyses of the primary safety variable are performed as exploratory analyses.

All of the above analyses of the primary safety variable are descriptive, without formal statistical tests being performed.

The analyses of secondary safety variables are similar to those for secondary efficacy variables, without any sequential order.

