	
• Severe renal impairment (eGFR < 30 mL/min/1.73 m²) or on dialysis, or post-TAVR unresolved acute kidney injury with renal dysfunction stage 2 or higher• Moderate and severe hepatic impairment (Child-Pugh Class B or C) or any hepatic disease associated with coagulopathy. 
Screening, IC and randomization:
 
Subjects are screened for inclusion after TAVR. Consenting subjects must be randomized within 1-7 days after a successful TAVR and before hospital discharge.

Study design	Event-driven, randomized, open-label with blinded endpoint evaluation, parallel-group, active-controlled, multicenter, international study
Methodology	
The primary comparison will be to test the superiority of a rivaroxaban-based strategy to an antiplatelet-based strategy with respect to the primary efficacy endpoint. This comparison is preceded by a non-inferiority test that must be satisfied.
 
Estimates of the hazard ratio for bleeding events together with their 95% confidence intervals will be calculated for descriptive purposes.

Type of control	Control treatment strategy is composed of active treatments and is in line with the current standard of care.
Clinical Event Committee	Yes
Data Safety Monitoring Board	Yes
Number of subjects	A total of 1520 subjects will be randomized.
Primary variable(s)	
Primary Efficacy Endpoint: death or first adjudicated thromboembolic event (DTE) defined as the composite of all-cause death and adjudicated any stroke, myocardial infarction (MI), symptomatic valve thrombosis, pulmonary embolism (PE), deep vein thrombosis (DVT), or non-CNS systemic embolism.
 
Primary Safety Endpoint: primary bleeding event (PBE) defined as the composite of adjudicated life-threatening, disabling or major bleeding, classified according to the valve academic research consortium (VARC) definitions following the bleeding academic research consortium (BARC) classification.

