Bleeding is a frequent periprocedural complication after TAVR, which has been shown to be associated with worse prognosis (21, 24-28). Although acute and sub-acute post-TAVR bleeding complications (up to 30 days) are linked to procedural or technical factors (e.g., vascular complications (29)), the impact of late bleeding events (after 30 days) in this population is still unclear. Data from the randomized cohorts and continued access registries in the PARTNER trials (27) suggest that major late bleeding complications occur in approximately 6% of patients between 30 days and 1 year, with GI and neurological bleedings being most frequent and are associated with an increased rate of death and morbidity. Independent predictors for late major bleeding events after TAVR included the presence of AF, moderate or severe residual paravalvular leak (PVL), presence of low baseline hemoglobin, and increased left ventricular mass.

Currently, dual-antiplatelet therapy (DAPT) with ASA and mainly clopidogrel for 3 to 6 months (if no indication for anticoagulation is present) is an empirical strategy widely accepted and incorporated as guideline recommendation for patients undergoing TAVR (26, 30-33). However, clopidogrel duration or loading dose is not specifically defined in guidelines, and lately the general usefulness of clopidogrel in combination with ASA in TAVR patients has been questioned (32, 34, 35). In two small non-randomized studies comparing DAPT to single-antiplatelet therapy (either ASA or clopidogrel), DAPT did not reduce the rate of cerebrovascular events but was associated with a higher rate of major and life-threatening bleeding complications (34, 36).

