Subjects randomized to rivaroxaban-based strategy: In the rivaroxaban-based strategy, rivaroxaban is started at the time of randomization if the subject is not on clopidogrel. If the subject is treated with clopidogrel, clopidogrel is stopped immediately after randomization and rivaroxaban is started within 1-3 days after the last intake of clopidogrel. In case study medication is started the next day post-TAVR, study medication should not be started earlier than the time the TAVR was done on the previous day and the subject should be stabilized and complications or bleedings should have been excluded carefully. Rivaroxaban 10 mg once-daily can be taken with or without food. ASA 75-100 mg once-daily is continued unchanged or started immediately after randomization if not already being taken.

Subjects randomized to antiplatelet-based strategy: In the antiplatelet-based strategy clopidogrel 75 mg once-daily and ASA 75-100 mg once-daily are to be continued unchanged, or to be started at the time of randomization if not already being taken. If clopidogrel is started at the time of randomization in a clopidogrel-naïve subject, a single loading dose of at least 300 mg should be administered followed by clopidogrel 75 mg once-daily.

For both strategies, the selection of the ASA dose (75-100 mg) is left at the discretion of the treating physician. In case the ASA dose before randomization was > 100 mg once-daily, the dose has to be decreased to 75-100 mg once-daily immediately after randomization.

In each strategy, one antiplatelet therapy agent is dropped after 90 days. This means that in the rivaroxaban-based strategy, ASA is discontinued after 90 days and rivaroxaban is to be continued. Whereas, in the antiplatelet-based strategy, clopidogrel must be discontinued after 90 days and ASA is to be continued.

Study treatments are continued until the efficacy cut-off date, i.e. when 440 subjects are anticipated to have experienced a positively adjudicated primary efficacy endpoint, when subjects will be transitioned from the assigned strategy to an appropriate therapy, as per the clinical site standard of care (Section [9.2.3](#)). This is anticipated to occur approximately 720

days after the first patient is randomized, but may vary depending on the recruitment rate as well as the on the primary efficacy event rate. One on-site visit will be scheduled for each patient when the efficacy cut-off date is anticipated.

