The plausibility of proportional hazards assumption will be assessed by visually comparing the plot of the log of cumulative hazard between treatments and by additionally adding a treatment by logarithm-transformed time interaction into the Cox model. If there is strong evidence of non-proportionality, the estimation of time-dependent hazard ratios will be considered.

All of the above analyses are carried out under the ITT data scope (i.e. all events are counted irrespective of the actual treatment at the time of the event).

Further details will be specified in SAP.

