6.2.1.3 Assessment plausibility of the proportional hazards assumption

If the hypothesis of non-inferiority is accepted the plausibility of the proportional hazards assumption will be assessed by visually comparing the plot of the log of cumulative hazard , in the ITT data scope, between treatments. The following SAS code may be used:

```
proc phreg data=work.infile (where=(treat=1));
model d2fDTE*DTE(0)=treat;
baseline out=work.ch_t1 cumhaz=ch;
run;
proc phreg data=work.infile (where=(treat=0));
model d2fDTE*DTE(0)=treat;
baseline out=work.ch_t0 cumhaz=ch;
run;
data work.log_ch;
set work.ch_t1
      work.ch_t0;
if ch ne 0 then log_ch=log(ch);
run;

proc sgrender data=work.log_ch template=comp_log_CH;
dynamic xvar="d2fDTE" yvar="log_ch" groupvar="treat";
run;

/*
where

```

```
work.infile = name of source dataset
treat       = randomization code
DTE         = death and thromboembolic event
d2fDTE     = days to first DTE (since randomization)
comp_log_ch = proc template for a log of cumulativehazards plot
*/

```

By additionally adding a time-varying covariate, an interaction between the predictor and the time the plausibility of proportional hazards is assessed, the following SAS code may be used:

```
proc phreg data= work.infile;
model d2fDTE * DTE (0)=treat treat_time;
treat_time = treat*log(d2fDTE);
proportionality_test: test treat_time;
run;
/*
where
work.infile = name of source dataset
treat       = randomization code
DTE         = death and thromboembolic event
d2fDTE     = days to first DTE (since randomization)
*/

```

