6.4.1 Analysis of the safety endpoints

6.4.1.1 Analysis of the primary safety endpoint

The descriptive analysis of the primary safety endpoint (PBE) and the secondary safety endpoints are performed on the FAS under the ITT scope

Kaplan-Meier curves, one-sided log rank p-value, number of patients with event and incidence rate are provided to evaluate the timing of event occurrence in the different treatment groups and the consistency of the respective treatment effects for all time points.. This is done analogue to the primary efficacy endpoint as described in section [6.2.1.2](#)

If the assumption of proportional hazards is plausible (see section [6.2.1.3](#)), Hazard ratio and corresponding two-sided 95% confidence intervals are estimated.. This is done analogue to the primary efficacy endpoint as described in section [6.2.1.2](#).

The analysis of the primary safety endpoint is visualized in [flowchart 3](#) in appendix I.

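### The synopsis promises the primary bleeding hazard ratio outright, but the analysis sections make it conditional on proportional hazards, with no fallback and no estimate split at the planned day-90 step-down

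*Protocol*

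**What the plan says.** Assessing PBE is one of the two primary objectives (Protocol 4.1). The documents describe its hazard ratio in three places.

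- Protocol Synopsis, Methodology: "Estimates of the hazard ratio for bleeding events together with their 95% confidence intervals will be calculated for descriptive purposes". No condition is attached.
- Protocol 10.3.7: "If the proportional hazards assumption holds for the primary safety variable, hazard ratio and corresponding two-sided 95% confidence intervals are estimated".
- SAP 6.4.1.1: "If the assumption of proportional hazards is plausible", with a pointer to SAP 6.2.1.3 for the check, and then estimation in the manner of SAP 6.2.1.2.

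SAP 6.2.1.3 opens with its own condition: "If the hypothesis of non-inferiority is accepted the plausibility of the proportional hazards assumption will be assessed". The check is a visual comparison of log cumulative hazards plus an interaction term, coded as "treat_time = treat*log(d2fDTE" and described in Protocol 10.3.5.1 as "adding a treatment by logarithm-transformed time interaction into the Cox model". No p-value or other rule defines what counts as plausible.

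Protocol 10.3.5.1 and SAP 6.2.1 mention time-dependent hazard ratios as an option under strong non-proportionality. Both are efficacy sections; Protocol 10.3.7 and SAP 6.4.1.1 do not repeat the option.

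On the regimens, Protocol 5.2 states: "In each strategy, one antiplatelet therapy agent is dropped after 90 days". Rivaroxaban plus ASA becomes rivaroxaban alone; clopidogrel plus ASA becomes ASA alone. No analysis is split at that day. The only time-split data scopes are before and after new-onset atrial fibrillation (NOAF).

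**The concern.** Amendment 3 removed the formal non-inferiority test for bleeding, so the descriptive hazard ratio and its interval are the main planned between-arm measure for the primary safety objective. Whether they appear depends on a judgement made after seeing the data, by an undefined standard, and possibly on the efficacy result.

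The day-90 step-down gives a reason, known in advance, to doubt a constant ratio. The Introduction (Protocol 3) adds that early bleeding is linked to procedural factors, and reports from two small non-randomized comparisons with single antiplatelet therapy that "DAPT did not reduce the rate of cerebrovascular events but was associated with a higher rate of major and life-threatening bleeding complications". So the condition could well come into play. The estimate would then be withheld or, if a change went unnoticed, a period average could be read as a constant effect.

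**Working it through.** **1. The plan's own figures.** The documents give no current sizing figure for bleeding. The efficacy design, which supplies the follow-up pattern used below, reproduces:

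- HR = ln(1 − 0.264) / ln(1 − 0.330) = 0.7654.
- Events = 4 × (1.960 + 0.8416)² / (ln 0.7654)² = 439.2, rounded up to 440. Power at 440 events is 80.1%.

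**2. What the safety sections deliver, read literally.**

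- Efficacy non-inferiority not accepted: SAP 6.2.1.3 does not run, so the condition in SAP 6.4.1.1 cannot be settled. SAP 6.2.1.2, the model for the estimation, also ties its Cox estimate to accepted non-inferiority.
- Check run, proportionality judged implausible: no PBE hazard ratio and no stated replacement. The cross-references in SAP 6.4.1.1 go to 6.2.1.2 and 6.2.1.3; the time-dependent option is in 6.2.1.
- Check run, proportionality judged plausible: one whole-period hazard ratio with its 95% interval.
- In every case: Kaplan-Meier estimates, event counts, incidence rates and a one-sided log-rank p-value.

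**3. Size of the averaging, as an illustration.** Piecewise-exponential bleeding times with a change at day 90; 760 per arm; follow-up uniform over 360-720 days (Protocol 10.4); 1000 simulated trials per row; death as a competing event and treatment discontinuation not modelled. These inputs are assumptions:

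- Control PBE risk of 6% or 12% at 540 days. The 12% appears only in text deleted by Amendment 3 (Protocol 15.2.2.30). The 6% borrows the Introduction's figure for major late bleeding between 30 days and 1 year.
- 17%, 33% or 50% of the control cumulative hazard to day 540 falls before day 90.
- True HR 1.0 to day 90 and 2.0 after. The documents give no source for any such pair.

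| Control risk | Early share | Events (by day 90) | Overall Cox HR | Log-time term p<0.05 | Day-90 term p<0.05 |
|---|---|---|---|---|---|
| 6% | 17% | 127 (16) | 1.83 | 19% | 25% |
| 6% | 33% | 120 (31) | 1.66 | 26% | 38% |
| 6% | 50% | 113 (46) | 1.49 | 31% | 42% |
| 12% | 17% | 249 (32) | 1.84 | 32% | 46% |
| 12% | 33% | 236 (63) | 1.66 | 48% | 64% |
| 12% | 50% | 224 (94) | 1.48 | 53% | 69% |

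Hand check of the fifth row: the overall log HR is roughly the event-weighted mean of the period log HRs, (173/236) × ln 2 = 0.508, and exp(0.508) = 1.66.

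Over all the changing-ratio patterns tried (1.0/1.5, 1.0/2.0, 0.8/2.0, 1.2/2.5), the log-time term reached p<0.05 in 9-76% of trials and the day-90 term in 10-91%. With a constant ratio of 1.0 or 1.5, both did so in about 3-7%.

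The average also moves with the stopping date. In a separate run at 12% control risk, cutting follow-up by 180 days moved the overall HR from 1.81 to 1.73 with a flat hazard, and from 1.61 to 1.50 with the early hazard tripled. The true effects were unchanged.

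**4. Precision of period estimates (fifth row).** With SE(log HR) ≈ 2/√events:

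- Early: 2/√63 = 0.252, so the 95% interval is the estimate times or divided by exp(1.96 × 0.252) = 1.64.
- Late: 2/√173 = 0.152, giving a factor of 1.35.

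**The case against.** The strongest reply is that little is lost. Kaplan-Meier curves, counts and incidence rates are unconditional and meant to show consistency over time. PBE has no formal test, so no error rate is affected. The trial compares strategies that include the step-down, so a whole-period hazard ratio is a legitimate average. All of this stands. A reader might infer that the safety objective could end with no estimate at all; the documents do not support that. What can be missing is a between-arm effect with an interval.

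A reader might also infer that the documents predict a shift at day 90, or that a single ratio would understate bleeding on long-term monotherapy. They do not. Both arms drop an antiplatelet agent, so evidence that dual therapy bleeds more than single therapy suggests less bleeding in the control arm later, but fixes neither the size nor the direction of any change in the ratio. Nor is day 90 a clean step: the visit window is ±15 days, and NOAF switches occur at other times.

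The log-time term is neither the only check nor blind to a step. A plot is planned too, and the p<0.05 rule in the table is not in the documents. A day-90 term is not uniformly better: for a change at day 30 (HR 1.0 then 2.0, 12% control risk, early hazard 3, 6 or 10 times the later one), the log-time term flagged 30%, 46% and 54% of trials, against 22%, 41% and 52%. That argues for adding a day-90 term, not for replacing the log-time term.

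Finally, SAP 6.4.1.1 models its analysis on efficacy, so the time-dependent option might be meant to carry over, and Flowchart 3 (primary safety), which is not reproduced in the text available, might show it. The written sections do not say so.

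**Conclusion.** The point holds as a conflict and a gap in the current text. The synopsis promises the PBE hazard ratio and interval; Protocol 10.3.7 and SAP 6.4.1.1 can withhold them, on an undefined criterion, through a check written to depend on the efficacy result, with no safety fallback. This rests on the wording alone.

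The size of any averaging rests on assumptions. If the true ratio were 1.0 to day 90 and 2.0 after, the overall figure would be 1.48-1.84 depending on when events fall, and the log-time term alone would reach p<0.05 in 19-53% of trials. Both outcomes are therefore realistic under such a shift: it is missed, or it is seen and the hazard ratio is dropped. Whether a shift exists is unknown. The primary efficacy test is not affected.

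**What to change.** - In Protocol 10.3.7 and SAP 6.4.1.1, delete the proportional-hazards condition, so that the overall PBE hazard ratio and 95% interval are always reported, as in the synopsis, and label them a whole-period average.
- State that the PBE proportionality check runs whatever the efficacy non-inferiority result.
- Keep the plot and the log-time term, and add a `treat*(time>90)` term beside them.
- Add, descriptively, PBE hazard ratios with 95% intervals for days 0-90 and after day 90, noting that the later one is conditional on being event-free at day 90.
- Add Kaplan-Meier PBE risks with intervals at 90 and 540 days.
- Leave the primary log-rank test unchanged.

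The cost is some wording and a few lines of code, with no new data and no effect on alpha. The downside is a little more output and an imprecise early-period hazard ratio.

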10.3.8. Subgroup analysis

Subgroup analyses for the primary efficacy and safety variables are based on the same analysis sets and data scopes as in the main analyses of the study outcome variables. The subgroup analyses are presented descriptively without formal hypotheses testing.

Homogeneity of treatment effect in subgroups, both in magnitude and direction, is assessed by adding a covariate for the subgroup variable and the corresponding treatment subgroup interaction to the respective Cox proportional hazards model used in the main analysis.

Additionally the hazard ratio for the treatment effect is estimated separately within each level of a subgroup variable using the same Cox proportional hazards.

As the number of subgroup analyses may be large, the probability of observing at least one spurious interaction is high despite the lack of a biological or pharmacological basis for expecting an interaction. Thus, any interactions with a p-value below the 5% type I error level in the analysis of primary variables will be interpreted as “flags” to prompt further investigation. This further investigation includes the likelihood ratio test proposed by Gail and Simon to test for qualitative interaction.

10.4. Determination of sample size

This section was modified with Amendment 3. For details, see Section 15.2.

The sample size determination for the study was driven by requirements for testing superiority of the rivaroxaban-based strategy over the antiplatelet-based strategy as described above.

The expected 540 days event rate of the primary efficacy endpoint is 33.0% (5-7, 10). The target Relative Risk at 540 days is 0.80, i.e. a reduction of the 540 days event rate from 33.0% under antiplatelet-based regimen to 26.4% under the rivaroxaban-based regimen. Under the assumption of an exponential distribution, the hazard ratio equals 0.7654.

Under the above assumptions, with 360 days accrual period, and an 540 days median follow-up (minimum 360 days and maximum 720 days), randomization of 2 x 740 analyzable subjects is expected to yield 440 primary events (196 in the rivaroxaban-based treatment group and 244 in the antiplatelet-based control group). This provides 80% power at a 5% significance level, without interim analyses for efficacy.

The power calculation was based on a test using the Cox proportional hazards model and was performed with PASS version 12.0.6, with the module for two survival curves using Cox's proportional hazards model.

A sample size of sample size of 2 x 760 subjects allows for an attrition rate of 2.63%. The study is event driven and the number of randomized subjects is estimated to be required to collect 440 primary efficacy events. The study is planned to run until this number of events has been reached or to stop earlier if the event rate is unexpectedly low.

With this sample size, the study has > 90% power to show non-inferiority with a non-inferiority margin of 1.20 if the underlying hazard ratio ≤ 0.90 at a one-sided significance level of 2.5%. The non-inferiority margin of 1.20 was selected based on clinical appropriateness.

The final sample size will depend on multiple factors including the rate of accrual of the primary endpoint events. The Steering Committee of the trial will monitor the aggregate (blinded) event rate and may increase the sample size or duration of follow-up to achieve the planned target number of events in consultation with the sponsor.

Non-inferiority margin

The non-inferiority margin of 1.20 for the HR for the efficacy comparison as described in Section 10.3.5.2 was selected based on both clinical appropriateness and relevant studies in the area of TAVR.

The event rates for mortality and ischemic events after TAVR are high. In high-risk subjects receiving TAVR in the PARTNER trial the composite of the rate of all-cause death or stroke was at 27% and 37% in the TAVR group after 1 and 2 years, respectively (14). The standard of care antithrombotic treatment after TAVR is dual antiplatelet therapy followed by single antiplatelet therapy with ASA although evidence from randomized control trials (RCTs) is lacking. Moreover, no prospective randomized studies to date have compared an active to no antithrombotic treatment in subjects after TAVR.

Earlier studies comparing TAVR with SAVR used a non-inferiority margin of 1.23 for RR of one year all-cause mortality (5, 10, 61).

In addition, NOAF is observed in up to 30% of subjects undergoing TAVR and has been demonstrated as single, independent predictor of stroke during the subacute phase after TAVR (13). Rivaroxaban has been approved for stroke prevention in non-valvular AF based on the positive results from the ROCKET AF trial (52), investigating rivaroxaban compared to VKA. In ROCKET AF a NI margin of 1.46 was applied but for a much lower event rate (2.2% per 100 patient years) than the one expected post-TAVR.

Taking into consideration both the historical NI margins used in TAVR trials together with the expected high event rates and the considerable proportion of subjects with NOAF after randomization, a non-inferiority margin of 1.20 was chosen for this study.

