5.3.3. Other variable(s)

This section was modified with Amendment 3. For details, see Section [15.2](#).

The individual components of the primary efficacy and safety endpoint will be assessed as other endpoints.

The mean transaortic valve pressure gradient at approximately 360 days after randomization as measured by routine echocardiogram (TTE or TEE), if available, will be captured in the eCRF and it is considered as an exploratory study endpoint.

End of study

The end of the study as a whole will be reached as soon as the last visit of the last subject has been reached in all centers in all participating countries.

The primary completion event for this study occurs when the 440th subject experiences a positively adjudicated primary efficacy endpoint or earlier if the event rate is unexpectedly low. The efficacy cut-off date is defined as the date of the primary completion event.

For practical purposes, the anticipated efficacy cut-off date is set based on a projection of the date of the primary completion event before 400 subjects have experienced a positively adjudicated primary efficacy endpoint. When the anticipated efficacy cut-off date is set, on-site visit will be scheduled for all subjects within 6 weeks.

The primary completion date for this study according to the FDA Amendment Act is specified in a separate document (not part of this study protocol).

6. Study population

This section was modified with Amendment 3. For details, see Section 15.2.

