10.3.5.1. Testing for superiority

This section was modified with Amendment 3. For details, see Section 15.2.

In order to evaluate whether the rivaroxaban-based strategy is superior to the antiplatelet-based strategy in prolonging the time to primary efficacy outcome event in patients with post-TAVR patients, the following null hypothesis (H_0) is tested at the significance level of 2.5%:

$H_0: S_{RIV}(t) = S_{APT}(t)$ for all time points $t \geq 0$, (i.e. “there is no difference between the rivaroxaban-based treatment group and the antiplatelet-based control group regarding the primary efficacy outcome for all time points”)

The one-sided alternative hypothesis is:

$H_1: S_{RIV}(t) > S_{APT}(t)$ for at least one time point $t \geq 0$, and $S_{RIV}(t) \geq S_{APT}(t)$ for all time points $t \geq 0$, (i.e. “there is a difference between the two groups in favor of the rivaroxaban-based treatment group regarding the primary efficacy outcome for at least one time point”)

where S_{RIV} denotes the event-free survival function of the rivaroxaban-based treatment group and S_{APT} denotes the event-free survival function of the antiplatelet-based treatment group.

The following decision rule to test the null hypothesis is applied:

According to the size of this study, it is justified to assume under H_0 a sufficiently close approximation of the one-sided log-rank test to the normal distribution. If the z-value from the one-sided log-rank test (for the difference $S_{RIV}(t) - S_{APT}(t)$) is larger than the critical quantile from the normal distribution ($z_{0.975} = 1.96$), the null hypothesis is rejected in favor of the alternative hypothesis.

Kaplan-Meier estimates of cumulative risk and cumulative hazard functions are provided to evaluate the timing of event occurrence in the different treatment groups and the consistency of the respective treatment effects for all time points.

Hazard ratio and corresponding two-sided 95% confidence intervals are estimated based on a Cox proportional hazards models. The parameter estimate β ($=\ln(HR)$), its standard error, p-value, and 95% Confidence Limits are calculated according to the maximum partial likelihood method, with Breslow's approximation for ties (phreg).

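### The 80% superiority power applies at 440 events, but the plan allows an earlier end with no floor, trigger or restated power; the stated non-inferiority power is not reached even at 440.

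*Protocol*

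**What the plan says.** Protocol 10.4 plans on "a reduction of the 540 days event rate from 33.0% under antiplatelet-based regimen to 26.4% under the rivaroxaban-based regimen" and adds: "Under the assumption of an exponential distribution, the hazard ratio equals 0.7654". With 740 analyzable subjects per arm the trial is "expected to yield 440 primary events (196 in the rivaroxaban-based treatment group and 244 in the antiplatelet-based control group"), and "This provides 80% power at a 5% significance level, without interim analyses for efficacy".

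The same section then allows two responses to a low event rate:

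- **Stop.** The study runs "until this number of events has been reached or to stop earlier if the event rate is unexpectedly low". Section 5.3.3 builds this into the primary completion event, which occurs at the 440th event "or earlier if the event rate is unexpectedly low". That event fixes the efficacy cut-off date, and so the data analysed.
- **Extend.** The Steering Committee watches the aggregate blinded event rate and "may increase the sample size or duration of follow-up to achieve the planned target number of events".

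Protocol 10.4 also claims more than 90% power for non-inferiority (margin 1.20, one-sided 2.5%) if the true hazard ratio is 0.90 or lower. Under Protocol 10.3.5 and SAP 6.2.1.1 that test uses on-treatment data.

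SAP 5.2.1 leaves the cut-off date to an Executive Committee and refers to Protocol 5.3.3, which names no such body.

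**The concern.** In an event-driven trial, power follows the final event count. Once the count may fall below 440, the 80% describes only one of the permitted endings, and a reader of 10.4 cannot tell what the others deliver. The same observation, a low pooled rate, can also lead to a smaller trial with less power or to a longer one that keeps about 80%. Neither 10.4, 5.3.3 nor the SAP says which.

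A low rate is plausible on the documents' own account. Section 3.1 describes a shift towards intermediate-risk patients with better outcomes. Section 6.1 excludes periprocedural stroke and other serious complications. The study rationale puts about half of the 30-day strokes in the first 24 hours, whereas randomization takes place 1–7 days after the procedure.

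At stake is a trial that ends without a clear answer although a true effect of the planned size exists. The non-inferiority test is the gate to the superiority test, so its power matters too.

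**Working it through.** **Inputs.** All are from Protocol 10.4 unless noted.

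- 540-day event rates of 33.0% and 26.4%; 440 events.
- 740 analyzable and 760 randomized subjects per arm.
- 360 days of accrual, with follow-up from 360 to 720 days.
- Superiority "is tested at the significance level of 2.5" per cent, one-sided, critical value 1.96 (Protocol 10.3.5.1). The 5% in 10.4 is therefore read as two-sided.
- Non-inferiority margin 1.20, hazard ratio 0.90, one-sided 2.5%.
- 1:1 allocation, so the log-rank variance is about d/4 for d events, as SAP 6.2.1.1 also notes.

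**Step 1: reproduce the plan's figure.**

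- HR = ln(1 − 0.264)/ln(1 − 0.330) = 0.7654.
- Power = Φ(|ln HR| × √d/2 − 1.96).
- At d = 440: 0.2674 × 10.488 − 1.96 = 0.844, and Φ(0.844) = 80.1%. The stated 80% reproduces.
- Events at a fixed 540 days: 740 × 0.330 + 740 × 0.264 = 244.2 + 195.4 = 439.6.
- With exponential times and uniform accrual, the expected proportion with an event is 1 − [exp(−360λ) − exp(−720λ)]/(360λ). This gives 243 + 194 = 437 events. Both agree with 440.

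**Step 2: superiority power below 440, same formula, HR 0.7654.**

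| Final events | Power |
|---|---|
| 440 | 80% |
| 418 | 78% |
| 400 | 76% |
| 350 | 71% |
| 300 | 64% |
| 250 | 56% |

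Power stays within two points of 80% down to about 418 events, and falls below 70% at 345.

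**Step 3: stop or extend under the same low rate.** The documents give no alternative rates, so the control rates here are assumptions. HR 0.7654, 740 per arm.

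| Assumed control rate at 540 days | Events if stopped at day 720 | Power | Study days to reach 440 without more subjects |
|---|---|---|---|
| 30% | 397 | 76% | 790 |
| 25% | 330 | 68% | 935 |
| 20% | 263 | 58% | 1152 |
| 15% | 197 | 47% | 1514 |

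Extending keeps about 80% at the planned hazard ratio.

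**Step 4: non-inferiority power at HR 0.90.**

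- Power = Φ(ln(1.20/0.90) × √d/2 − 1.96), with ln(1.20/0.90) = 0.2877.
- At 440 events: 0.2877 × 10.488 − 1.96 = 1.057, giving 85.5%.
- With a 33.0% control rate, HR 0.90 and the planned follow-up, the Step 1 formula gives 465 events for 740 per arm and 478 for 760 per arm. Power is 87.4% at 465. At 478 it is Φ(0.2877 × 10.932 − 1.96) = Φ(1.185) = 88.2%.
- For 90%: d = 4 × (1.960 + 1.282)²/0.2877² ≈ 508 events.
- At HR 0.7654 and 440 events the figure is 99.7%, so the claim fails near the 0.90 boundary that it names.

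These counts include every event. The test censors two days after permanent discontinuation, so fewer events would normally count and power would be lower. The documents give no expected on-treatment count.

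**The case against.** The strongest reply is that the plan is more disciplined than it looks. The Amendment 3 rationale (Protocol 15.2.1.12) reserves early ending for a rate far below expectation, with 440 events projected well after the start of 2018. It says the overall event rate and total time at risk will be considered, holds the treatment effect at its planned value, and warns that longer follow-up may dilute the effect. On that reading a modest shortfall leads to extension and a severe one to stopping. This deserves weight: the choice is not unguided. But the guide contains no event count or rate, and it is not carried into 10.4, 5.3.3 or the SAP.

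Four stronger readings are tempting, and the documents do not support them.

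- **That the plan orders an extension and so contradicts itself.** The Committee may extend. These are two unranked permissions.
- **That the 80% claim is false.** It is conditional on the planned event rates and an expected 440 events, and under those conditions it is correct.
- **That the 33% rate comes only from high-risk and inoperable patients.** The introduction describes the CoreValve trial population as intermediate-to-high risk, and no event rate is given for patients who remain after this trial's exclusions. A low rate is plausible but cannot be quantified.
- **That early ending inflates type I error.** The monitored rate is aggregate and blinded, no formal interim analysis is planned, and endpoint adjudication is blinded to allocation.

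It is also fair to say that the non-inferiority shortfall is not caused by early stopping, since it is present at 440 events.

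**Conclusion.** The point holds as an incomplete power statement with unranked options. The 80% applies at 440 events and is nearly kept down to about 418. Below that the loss is material: 76% at 400, 71% at 350, 64% at 300 and 56% at 250. No minimum count, numeric trigger, resulting power or order of precedence is stated.

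The non-inferiority claim of more than 90% at a hazard ratio of 0.90 is not met: about 85% at 440 events and 87–88% at the expected 465–478, against about 508 needed, with on-treatment censoring lowering it further.

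These figures assume proportional hazards, 1:1 allocation and the normal approximation to the log-rank test. The expected counts also assume exponential event times and uniform accrual. The consequence is reduced power and a greater chance of an inconclusive trial.

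**What to change.** **In Protocol 10.4:**

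- Say that 80% power applies at 440 events, and tabulate superiority power by final event count as in Step 2.
- Replace the non-inferiority figure with one computed on the expected on-treatment event count, stating the assumed discontinuation.

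**In Protocol 10.4 and 5.3.3 and SAP 5.2.1:**

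- Reconcile the stop and extend sentences by stating which takes precedence, with a trigger fixed in advance (an event count, a pooled rate or a projected calendar date).
- Assign the decision to one named body, used consistently in both documents, and limit it expressly to blinded pooled counts. At present the blinding wording is attached only to the extension sentence, and the trial is open-label.
- Record the projected event count and resulting power when the decision is made.

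The extension option need not be deleted. Removing it would lock in lower power under a low rate, and whether to stop or extend is the sponsor's trade-off.

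**Cost:** wording changes in two documents and a less favourable stated power. No extra patients are needed.
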